6.3.5 Restarting or reinstating previous dose

Dosing of ruxolitinib may be restarted or increased following recovery of platelet counts and/or ANC to acceptable levels as illustrated in [Table 6-3](#). The objective for restarting or

escalating after a reduction for safety is to find the highest safe dose of ruxolitinib for each patient, with increases in dose generally not more than in increments of 5 mg BID and not more often than every 2 weeks. Similarly, ANC levels that decline to < 500/ μ L necessitate immediate dose interruption ([Section 6.3.1.1](#)). ANC level recovery to 500 / μ L and above but less than 750/ μ L will allow dosing to be restarted at 5 mg BID, and ANC levels between 750/ μ L, but < 1000/ μ L may restart at 10 mg BID. Absolute neutrophil count level increases to above 1000/ μ L will allow a further dose increase.

[figure not shown]
After restarting using the guidelines in [Table 6-3](#), if it is found that a patient cannot tolerate the lowest allowed dose (5mg BID, or 5mg QD with concomitant CYP3A4 inhibitor, see [Section 6.4.2](#)) without platelets falling below 25,000/ μ L, neutrophils falling below 500/ μ L, or Hgb falling below 6.5g/dL despite the use of transfusion therapy, drug must be permanently discontinued ([Section 6.3.1.1](#)).

Table 6-3 Restarting or reinstating previous ruxolitinib dose after safety interruptions or dose reductions

Current Platelet Count after interruption or reduction	Maximum Dose for Restarting or reinstating previous dose after interruption or reduction
< 25,000/ μ L	Continue hold
25,000/ μ L to < 50,000/ μ L	5 mg BID
50,000/ μ L to < 75,000/ μ L	10 mg BID
75,000/ μ L to < 125,000/ μ L	15 mg BID
\geq 125,000/ μ L	20 mg BID
Current ANC Level after interruption or reduction	Dose Restart or Dose Increase Guidelines
< 500/ μ L	Continue hold
500 to < 750/ μ L	5 mg BID for at least 2 weeks; if stable, may increase to 10 mg BID
750 to < 1000/ μ L	10 mg BID for at least 2 weeks; if stable, may increase to 15 mg BID
1000 to < 1500/ μ L	15 mg BID for at least 2 weeks; if stable may increase to 20 mg BID
\geq 1500/ μ L	20 mg BID
NOTE: Whether the dose interruption occurred because of neutropenia, thrombocytopenia or both, when restarting, both the platelet count and ANC must be considered to determine the restart dose, with the lower calculated dose being used.	

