6.3.1.1 Dose modification for hematologic toxicity

For all patients who receive ruxolitinib, there are mandatory dose decreases or dose interruptions for declining platelet counts, hemoglobin or ANC levels that might be observed while on ruxolitinib therapy. Deviations to mandatory dose interruptions and/or reductions are not allowed.

Doses may be titrated based on safety. Dosing must be held if platelet counts decline below 25,000/ μ L or if ANC that is \leq 500/ μ L or Hemoglobin is \leq 6.5 g/dL despite transfusions, while receiving ruxolitinib.

After dose interruption, when blood counts recover, dosing must be restarted at 5 mg twice daily and gradually increased based on careful monitoring of blood cell counts.

Table 6-2 Dose modifications for hematologic toxicity

[figure not shown]
The instructions provided in this table and the criteria for dose reduction / interruption are used to determine a protocol deviation.

Hematology Value at time of decline:	Dose at the time of decline				
	25 mg BID	20 mg BID	15 mg BID	10 mg BID	5 mg BID
	Dose reduction to				
Platelet < 125,000 / μ L	20 mg BID	20 mg BID	15 mg BID	10 mg BID	5 mg BID
Platelet < 100,000 / μ L	15 mg BID	15 mg BID	15 mg BID	10 mg BID	5 mg BID
Platelet < 75,000 / μ L	10 mg BID	10 mg BID	10 mg BID	10 mg BID	5 mg BID
Platelet < 50,000 / μ L	5 mg BID	5 mg BID	5 mg BID	5 mg BID	5 mg BID
Platelet < 25,000 / μ L	Treatment must be interrupted.				
Hemoglobin \leq 6.5 g/dL despite transfusions	Treatment must be interrupted.				
Absolute neutrophil count < 0.5 x 10 ⁹ /L	Treatment must be interrupted.				

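### After a mandated hold, Section 6.3.1.1 requires restart at 5 mg BID, while Section 6.3.5 and the Table 6-3 ANC rows allow or give 10 to 20 mg BID, and no text says which rule governs

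*Protocol*

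**What the plan says.** Protocol Section 6.3.1.1 mandates a hold for low platelets (below 25,000/µL), low ANC (500/µL or less), or hemoglobin of 6.5 g/dL or less despite transfusions. It then says that "dosing must be restarted at 5 mg twice daily and gradually increased". The restart dose does not depend on the recovered count.

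Section 6.3.5 opens by saying that dosing "may be restarted or increased following recovery of platelet counts and/or ANC to acceptable levels as illustrated in" Table 6-3. Its text restarts patients at ANC 500 to <750/µL at 5 mg BID and says that those at 750 to <1000/µL "may restart at 10 mg BID". Above 1000/µL it speaks only of a further increase and names no dose.

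Table 6-3 is titled "Restarting or reinstating previous ruxolitinib dose after safety interruptions or dose reductions". Its platelet column is headed "Maximum Dose for Restarting or reinstating previous dose after interruption or reduction". The ANC column is headed as restart or increase guidelines and is not labelled a maximum; one row reads "10 mg BID for at least 2 weeks; if stable, may increase to 15 mg BID". The note below the table covers interruptions for neutropenia, thrombocytopenia or both, and takes the lower of the platelet and ANC doses as the restart dose.

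Section 6.3.3 refers the reader to Section 6.3.6 for reinstating dose after a hold. Section 6.3.6 is about overdose; the restart rules are in Section 6.3.5.

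**The concern.** Two safety rules can give different doses to the same patient, just recovered from a severe cytopenia. A site that reads Section 6.3.1.1 restarts at 5 mg BID. A site that reads Section 6.3.5 and Table 6-3 may restart at 10 mg BID or more and then departs from the word *must* in Section 6.3.1.1. The trial's rationale is that a lower dose spares hematopoiesis, so the restart dose should not depend on which section a site opens. The section that should direct the reader points to the wrong place.

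**Working it through.** The plan gives no figure on this point, so the check is a comparison of the rules followed by a count.

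**1. Can Table 6-3 be read as applying only after a 5 mg BID restart?** Not on its wording. The ANC sentence speaks of restarting, the table title includes interruptions, the note uses the table to fix the restart dose, and Section 6.3.5 later says "After restarting using the guidelines in" Table 6-3.

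**2. Restart dose under Table 6-3.** Inputs are the first dose named in each row in which dosing may resume. Dose = min(platelet row, ANC row), in mg BID:

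| Platelets /µL (maximum) | ANC 500 to <750 (5) | 750 to <1000 (10) | 1000 to <1500 (15) | ≥1500 (20) |
|---|---|---|---|---|
| 25,000 to <50,000 (5) | 5 | 5 | 5 | 5 |
| 50,000 to <75,000 (10) | 5 | 10 (tie) | 10 (platelet) | 10 (platelet) |
| 75,000 to <125,000 (15) | 5 | 10 (ANC) | 15 (tie) | 15 (platelet) |
| ≥125,000 (20) | 5 | 10 (ANC) | 15 (ANC) | 20 (tie) |

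- 5 mg BID: 7 cells, in agreement with Section 6.3.1.1.
- Above 5 mg BID: 5 + 3 + 1 = 9 cells (10, 15 and 20 mg BID respectively).
- Of the 9, the ANC row is strictly lower in 3 and ties in 3, so it sets or ties the dose in 6. The platelet row is strictly lower in 3. Because the platelet row is a maximum, 5 mg BID complies there.

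These are counts of table cells, not probabilities.

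**3. Size of the dose gap.** 10/5 = 2-fold, 15/5 = 3-fold, 20/5 = 4-fold. Assuming no restart above the pre-hold dose, the gap is at most 2-fold up to Week 12, because the dose until then is 10 mg BID. A 3-fold gap needs a prior dose of at least 15 mg BID (targeted from Week 12). A 4-fold gap needs at least 20 mg BID (targeted from Week 16).

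**4. Time to catch up from 5 mg BID.** Section 6.3.5 generally allows increases of up to 5 mg BID, no more often than every 2 weeks. To reach 10, 15 or 20 mg BID: (10−5)/5 × 2 = 2 weeks; (15−5)/5 × 2 = 4 weeks; (20−5)/5 × 2 = 6 weeks.

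**5. Number of patients** (assumption: earlier myelofibrosis rates apply, although this trial starts at 10 mg BID and admits platelets from 50,000/µL).

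- ANC: the appended label (Section 4.8) reports holding or reduction for neutropenia in 1.0% of phase 3 patients, and protocol Section 1.2.1.2.3 gives 1% for COMFORT-II. 0.010 × 50 = 0.5 patient. This includes reductions, and a conflict also needs a restart at ANC ≥750/µL with platelets ≥50,000/µL. The range is 0 to about 0.5.
- Platelets: grade 4 thrombocytopenia in the phase I/II study was 0% at 10 and 15 mg BID and 6% at 25 mg BID, so 0 to 0.06 × 50 = 3 patients with such an event. This does not count conflicts, for the reasons given under the objection.

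**The case against.** The strongest reply is that a compliant dose exists under most of the wording. The ANC sentence is permissive and names only 10 mg BID, and the platelet column is a ceiling, so 5 mg BID satisfies both as well as Section 6.3.1.1. That stands, and it removes 3 of the 9 cells. It does not remove the other 6: there the ANC row names a dose above 5 mg BID that is not labelled a maximum, and the note makes it the restart dose. A site using the permission in the ANC sentence also still departs from Section 6.3.1.1.

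A second reply is that recovery will usually be seen first in the low rows, where both rules give 5 mg BID, since Section 6.3.3 recommends counts at least twice weekly below 50,000/µL platelets or 500/µL ANC. This is often true. But restart is not required at the first qualifying count, holds may generally last up to 8 weeks, and Section 6.4.2 allows granulocyte growth factors for severe neutropenia during a hold. A restart at ANC ≥750/µL is therefore possible.

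A reader might infer that up to 3 patients with platelet holds are also in conflict. The documents do not support that. The 3 assumes all 50 patients at 25 mg BID, which Section 6.2.3 allows only from Week 20, in non-responders with platelets ≥200 × 10⁹/L. After a platelet hold with ANC ≥1500/µL, the ANC row sets or ties the dose above 5 mg BID only if platelets are already ≥125,000/µL at restart.

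For a hemoglobin hold the reading is arguable. Table 6-3 has no hemoglobin row and its note names only neutropenia and thrombocytopenia, but its title covers safety interruptions generally. The point does not rest on that case.

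**Conclusion.** The two rules conflict, and the documents do not resolve it. The true conflict covers 6 of the 16 combinations in which dosing may resume, with a gap of 2- to 4-fold. Few patients are likely to meet it: probably under 1 of 50 for ANC holds, if earlier myelofibrosis rates carry over. No firm count can be given for platelet holds.

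A reader might infer that the primary result is at risk, because a patient restarted at 5 mg BID could still be catching up at Week 24. The documents do not support that. The FAS includes every assigned patient who took a dose, the SAP's per-protocol exclusions (Section 2.2.3) list no dosing rule, and so few patients give no basis for claiming a measurable effect on the response rate. Nor does the text make a 10 mg BID restart a disallowed deviation or an overdose: the ban on deviations in Section 6.3.1.1 names interruptions and reductions, not restarts, and Section 6.3.5 itself permits that dose. This is a minor correction for patient safety and consistency between sites.

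**What to change.** Make 5 mg BID the governing restart dose after a hold mandated in Section 6.3.1.1. It is the more cautious dose, it keeps the existing requirement, the appended label (Section 4.2) names the same restart dose as an option, and it settles hemoglobin holds.

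1. In Section 6.3.5 add: *After a hold mandated in Section 6.3.1.1, dosing restarts at 5 mg BID (5 mg QD with a concomitant strong CYP3A4 or dual CYP2C9/CYP3A4 inhibitor), whatever the recovered count. Table 6-3 then limits reinstatement towards the previous dose, and it governs reinstatement after a reduction and restart after any other safety interruption.* The QD provision follows the lowest dose that Section 6.3.5 already recognises ("5mg BID, or 5mg QD with concomitant CYP3A4 inhibitor").
2. In the ANC sentence of Section 6.3.5, change "may restart at 10 mg BID" to *may increase to 10 mg BID after restart*. In the Table 6-3 note, call the lower of the two doses *the maximum dose* instead of the restart dose.
3. In Section 6.3.3, change the reference from Section 6.3.6 to Section 6.3.5.

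Keep the 2-week ANC step-ups in Table 6-3, the word *generally* in the increment rule, and the Section 6.2.3 escalation up to 25 mg BID; none of these needs to change to remove the conflict.

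The cost is a short amendment and a note to sites. Patients who recover well would reach their Table 6-3 dose about 2 to 6 weeks later. If the sponsor prefers Table 6-3 to govern, it should instead limit the requirement in Section 6.3.1.1 to hemoglobin holds.

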6.3.6 Treatment of investigational drug overdose

There is no known antidote for ruxolitinib overdose. Overdose will be defined as the use of ruxolitinib in doses in excess of that specified in the protocol. . Patients overdosed should be treated with appropriate supportive care until recovery. Use of ruxolitinib in doses in excess of that specified in the protocol should not be recorded in the eCRFs as an AE of ‘Overdose’. An overdose with associated SAEs should be recorded as the SAE diagnosis/symptoms on the relevant AE and SAE forms in the eCRFs. An overdose with associated non-serious AEs should be recorded as the AE diagnosis/symptoms on the relevant AE forms in the eCRFs. An overdose without associated symptoms should not be recorded as an AE in the eCRFs.

6.4 Concomitant medications

All concomitant medications and treatments must be recorded on the appropriate eCRF. Any prior medication received up to 30 days prior to the first dose of study drug will be recorded in the CRF. All prior medications used to treat myelofibrosis will be recorded.

Patients will be instructed not to take any additional medications (including over-the-counter products) during the course of the study without consultation with the investigator.

6.4.1 Permitted concomitant therapy

The patient must be told to notify the investigational site about any new medications he/she takes after the start of the study drug. At each visit, the patient must be asked about any new medications he/she is or has taken. All medications (other than study drug) and significant non-drug therapies (including physical therapy, herbal/natural medications and blood transfusions) administered during the study must be listed on the appropriate CRF.

All medications taken ≤ 30 days prior to study entry should be recorded on the appropriate Case Report Form (eCRF). All prior medications used to treat PMF, PPV MF, or PET-MF will be recorded. All concomitant treatments during the trial will also be recorded in the eCRF.

The following restrictions apply during the study:

- No other investigational therapy should be given to patients.
- No anticancer agents other than the study medication (ruxolitinib) should be given to patients until disease progression or withdrawal from the study. If such agents are required for a patient then the patient must first be withdrawn from the study.

6.4.2 Permitted concomitant therapy requiring caution and/or action

The following medications have restrictions on use, dose, or require changes to the way in which ruxolitinib is administered during the study:

- In patients for whom warfarin or heparin use will be initiated, the degree of thrombocytopenia should be considered, coagulation parameters monitored, and dose of anticoagulant adjusted accordingly. If anticoagulation is required during ruxolitinib administration, low molecular weight heparin is preferred, particularly in patients who are: elderly, history of CHF, diabetic, hepatic or renal disease, or atrial fibrillation (first episode).
- Low dose aspirin (≤ 150 mg/day) and non-steroidal anti-inflammatory agents (acetaminophen, ibuprofen) may be used. Aspirin doses > 150 mg are prohibited.
- Inducers or inhibitors of the metabolizing enzyme CYP3A4 (Appendix 5)
- When concomitant administration of a strong (potent) inhibitor of CYP3A4 metabolizing enzymes or dual CYP2C9/CYP3A4 inhibitors (Appendix 5) is required for patient management, the dose of ruxolitinib tablets must be reduced by approximately 50% to be administered twice daily by decreasing the twice daily dose or by decreasing the frequency of dosing to the corresponding once daily dose when twice daily dose is not practical.
 - Note: No dose adjustment of ruxolitinib is needed for use with topical ketoconazole.

- Note: More frequent monitoring of hematology parameters and clinical signs and symptoms of ruxolitinib related adverse reactions is recommended upon initiation of a strong (potent) CYP3A4 inhibitor.
- No dose adjustment will be made when moderate systemic CYP3A4 inducers ([Appendix 5](#)) are co-administered with study treatment.
- Granulocyte growth factors are not allowed while study treatment is being administered but may be used for severe neutropenia at the Investigator's discretion while study medication is being withheld.
- Certain herbal supplements see [Appendix 5](#) are prohibited. Because the composition, pharmacokinetics and metabolism of many herbal supplements are unknown, the concurrent use of all herbal supplements is strongly discouraged during the study however if used during the trial please ensure the treatment is entered on the proper eCRF page (see [Section 6.4.1](#)).

6.4.3 Prohibited concomitant therapy

The following medications are prohibited during the study until treatment discontinuation:

- Concomitant use of another JAK inhibitor.
- Any investigational medication (other than ruxolitinib) that is not approved for any indication. Use of such medications within 30 days or 5 half-lives, whichever is longer, prior to the first dose of study drug and until treatment discontinuation is prohibited.
- Use of hydroxyurea, interferon, thalidomide, busulfan, lenalidomide, or anagrelide is not permitted at any time during participation in the study. These medications should be discontinued prior to Day 1 of ruxolitinib therapy. All adverse events attributed to these medications should be resolved prior to Day 1 of ruxolitinib treatment.
- Potent inducers of CYP3A4 ([Appendix 5](#)) are not permitted.
- Aspirin in doses exceeding 150 mg per day is prohibited.

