2.3 Rationale for dose and regimen selection

Phase I/II trials evaluated a number of different doses and schedules of ruxolitinib. Based on these, two phase III trials evaluated the efficacy and safety of ruxolitinib versus placebo in COMFORT I and versus BAT in COMFORT II in a population of patients with primary and secondary MF. In both phase III trials a starting dose of 20 mg orally BID was administered for patients with platelet counts from 200,000/ μ L and a lower starting dose of 15 mg orally BID in patients with baseline platelet counts from 100,000 to 200,000/ μ L.

Additional studies generated clinical data on the efficacy and tolerability of ruxolitinib in patients with MF and platelet counts from 50,000 to 100,000/ μ L. A starting dose of 5 mg BID with subsequent optional up titrations every 4 weeks by dose increments of 5 mg OD was evaluated in a phase II open label single arm study INC B18424-258 in a population of patients with platelet counts from 50,000 to 100,000/ μ L. Similarly, an expanded access program and phase IIIb study CINC424A2401 (JUMP) that recruited more than 2200 patients allowed the inclusion of patients with low platelet counts (50,000 to 100,000/ μ L) to be treated with a 5 mg BID starting dose.

Furthermore, a Phase Ib study (EXPAND) evaluating the safety and MTD of ruxolitinib in patients with lower baseline platelet counts (50,000– 100,000/ μ L) suggests that higher doses of ruxolitinib can be safely administered to patients with lower baseline platelet count. The maximum safe starting dose in this ongoing study was reported to be 15 mg BID for patients with platelet counts from 75,000 to 100,000/ μ L and 10 mg BID for patients with platelet counts from 50,000 to 75,000/ μ L.

Anemia may be ameliorated by lowering the dose of ruxolitinib or by concomitant use of erythropoietin stimulating agents and/or anabolic steroids (Reilly 2014). This approach may make particular sense in patients with anemia at the moment of treatment initiation with ruxolitinib in order to avoid further hemoglobin decrease, the need of blood transfusions or have them more frequently in patients already receiving regular transfusions for anemia.

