2.7.2 Statistical hypothesis, model, and method of analysis

The spleen length response rate at Week 48 will be evaluated. The point estimate of the proportion of patients achieving $\geq 50\%$ reduction in spleen length at Week 48 along with corresponding exact 95% confidence interval using Clopper and Pearson exact method will be presented.

Percent change from baseline in spleen length over time will be evaluated to assess the effect of ruxolitinib on spleen length. The analysis will be performed for each visit and at end of treatment. This parameter is computed by dividing the difference of spleen length at assessment time and at baseline by the length at baseline multiplied by one hundred.

To evaluate the effect of ruxolitinib on transfusion requirements, the following will be summarized:

- Number and percentage of transfusions over time
- Proportion of patients who are transfusion dependent (TD). Transfusion dependence is defined as per IWG-MRT criteria: 6 or more units of transfusion in 12 weeks prior to baseline.
- For transfusion dependent (TD) patients at baseline, the following will be analyzed:
 - transfusion independence (TI) rate (requiring no unit of transfusion for ≥ 12 weeks at any time during the study)
 - transfusion response rate (not TD: having 5 or less units of transfusion for ≥ 12 weeks at any time during the study)
- For patients who were not transfusion dependent (TD) at baseline, the following will be analyzed:
 - transfusion dependence (TD) rate (requiring 6 or more units of transfusion for ≥ 12 weeks at any time during the study)

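### The transfusion rates take no account of erythropoiesis-stimulating agents or anabolic steroids started on study, so improvement due to these agents could be attributed to the dosing regimen

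*Protocol*

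**What the plan says.** **Concomitant drugs.** Under Protocol 6.4, patients may not add medication "during the course of the study without consultation with the investigator"; that requires consultation and does not ban new drugs. Protocol 6.4.1 bars other investigational therapy and adds: "No anticancer agents other than the study medication (ruxolitinib) should be given to patients until disease progression or withdrawal from the study". The only growth-factor restriction is in 6.4.2: "Granulocyte growth factors are not allowed while study treatment is being administered". Protocol 6.4.3, whose list opens with "The following medications are prohibited during the study until treatment discontinuation", also bars other JAK inhibitors, potent CYP3A4 inducers, aspirin above a stated dose and six named agents: "Use of hydroxyurea, interferon, thalidomide, busulfan, lenalidomide, or anagrelide is not permitted at any time during participation in the study". ESAs, androgens and anabolic steroids appear in none of these places. The entry criteria in 5.2 and 5.3 require neither washout nor stable use of them.

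**What the protocol says about these agents.** Section 2.3, repeated in 6.2.1, states: "Anemia may be ameliorated by lowering the dose of ruxolitinib or by concomitant use of erythropoietin stimulating agents and/or anabolic steroids". Section 1.1 lists ESAs and androgens among available myelofibrosis treatments, alongside thalidomide and hydroxyurea; 6.4.3 bans the last two and does not mention the first two. The product information in Appendix 6 (section 4.5) says that concurrent haematopoietic growth factors have not been studied with the drug.

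**Endpoints.** SAP 2.7.2 defines three rates:
- Transfusion independence (TI), in patients transfusion dependent (TD) at baseline: "requiring no unit of transfusion for" at least 12 weeks, at any point on study.
- Transfusion response, in the same patients: no more than 5 units over such a period.
- New transfusion dependence, in patients not TD at baseline: 6 or more units over such a period.

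None of the three has a condition on other anemia treatment.

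**The concern.** Protocol 2.2 asks whether starting low and titrating up can limit hemoglobin decline and transfusion need, and 2.6 names lower transfusion need as part of the main expected benefit. Section 2.3 gives two ways to ease anemia: a lower ruxolitinib dose, which is the regimen under study, or adding an ESA or anabolic steroid. If the second happens on study, the analysis cannot tell it from the first. There is no control arm in which the same supportive treatment would appear.

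The definitions add to the exposure. One qualifying window is enough, and the planned minimum treatment of 48 weeks (Protocol 6.1.5) holds 48 / 12 = 4 non-overlapping windows, so there is time to start an agent and then qualify. Use is plausible: every patient enters with hemoglobin below 10 g/dL, and Appendix 6 reports that 79.3% of such patients fell below 8 g/dL on treatment, against 30.1% of those starting higher.

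At stake is the interpretation of the TI and response rates, which could look too high, and of the new-TD rate, which could look too low.

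**Working it through.** **Step 1: does any other part of the plan deal with it?**
- Recording: yes. Protocol 6.4 and 6.4.1 require all concomitant treatment to go into the eCRF.
- Reporting: SAP 2.4.2 gives a listing and a frequency table by ATC class, with no link to any endpoint.
- Per-protocol set: the exclusions in SAP 2.2.3 include the six named agents but not ESA or anabolic steroid use, and the set is specified only for repeating the primary analysis (SAP 2.5.4).
- Subgroups: none (SAP 2.2.4).

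So the information exists, but no visible prespecified analysis uses it.

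**Step 2: the plan's own figures.** The documents state no figure for the transfusion endpoints. Those for spleen response reproduce: with 50 patients and success at 13 or more responders, the exact binomial gives 0.0301 at a true rate of 15% and 0.9339 at 35%. With the Beta(1/3, 1) prior, the posterior probability of a rate of 15% or less at 13/50 is 0.0243. Nothing in this point changes them.

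**Step 3: possible size.** The documents give neither usage nor effect rates, so all three inputs are assumptions, for patients TD at baseline:
- t: TI rate due to the regimen alone (0.10 to 0.30)
- u: share who start an ESA or anabolic steroid (0.10 to 0.30)
- g: chance that the agent turns an otherwise non-TI patient into a TI patient (0.2 or 0.4)

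Reported TI rate = t + (1 − t) × u × g, so the upward bias is (1 − t) × u × g.

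| t | u | Reported, g = 0.2 | Reported, g = 0.4 |
|---|---|---|---|
| 0.10 | 0.10 | 0.118 | 0.136 |
| 0.10 | 0.30 | 0.154 | 0.208 |
| 0.20 | 0.10 | 0.216 | 0.232 |
| 0.20 | 0.30 | 0.248 | 0.296 |
| 0.30 | 0.10 | 0.314 | 0.328 |
| 0.30 | 0.30 | 0.342 | 0.384 |

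Smallest bias: (1 − 0.30) × 0.10 × 0.2 = 0.014. Largest: (1 − 0.10) × 0.30 × 0.4 = 0.108. The range is about 1 to 11 percentage points. With u = 0 or g = 0 the bias is zero.

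**The case against.** **No decision depends on these rates.** They are secondary, with no test, threshold or power statement (Protocol 10.9; SAP 2.6, 2.7.2). Table 3-1 words the objective as the effect of ruxolitinib on transfusion requirements, not of the regimen. This stands, and it limits the severity. It does not remove the point, because Protocol 2.2 and 2.6 put the transfusion question to the regimen.

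**The agents are visible in the report.** The listing and ATC table show who took them. This stands too, but matching those listings to the endpoint after results are known is no substitute for a rule set beforehand.

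**The effect on ruxolitinib is uncertain.** Appendix 6 says it is not known whether JAK inhibition reduces the efficacy of haematopoietic growth factors. Section 2.3 indicates a direction but no size. A reader might infer a certain or large inflation, such as a halving of the TI rate; that would need invented counts of dependent patients, responders and users.

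**Counting outcomes whatever supportive care was given is legitimate.** Agreed. This is a reason to keep the unrestricted rates and report a restricted version beside them.

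**Redaction.** Some exploratory objectives and analyses are blacked out, so a related analysis cannot be excluded entirely. The transfusion definitions themselves are fully visible.

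**Conclusion.** The gap is real and modest. ESAs and androgens/anabolic steroids are not prohibited, by omission rather than by stated permission. The protocol itself says they may ease anemia, and none of the three transfusion rates allows for a patient starting them. Improvement due to these agents could therefore be attributed to the lower start and titration. Over the assumed inputs the TI rate is too high by about 1 to 11 percentage points, and by nothing if no one starts these agents. The size for transfusion response and new TD was not computed.

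A reader might go further and infer that the trial could wrongly declare success, or that the agents go unrecorded. The documents support neither: the only success rule concerns spleen length, and all concomitant treatment is recorded. Whether these agents should be allowed is a clinical question outside this point.

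**What to change.** Leave permitted care and the unrestricted rates as they are. Add to SAP 2.7.2 a prespecified analysis reported beside them:

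- **TI and transfusion response:** a 12-week window does not count if an ESA or androgen/anabolic steroid was started or increased during it. Nor does it count if this happened on study before the window and the agent is still in use, or was stopped within a carry-over period fixed in advance. Windows before any start, windows on unchanged pre-study use, and windows after the carry-over period still count, so a brief course does not bar a patient for good.
- **New TD in patients not dependent at baseline:** report the rate by use of these agents, and again with starters counted as failures.
- **Hemoglobin:** show it over time by use of these agents.

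The cost is SAP wording, a drug-class list and a little programming on data already collected. The restricted rates may look less favourable and will under-credit some patients who would have improved anyway; the paired unrestricted rate makes that visible.
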